 - Study personnel with direct subject contact are required to complete Blood borne Pathogens and Infection Control training annually.

Medical Personnel Training

All study nurses will be currently licensed RNs. All RNs that are employed by the study are oriented to the care of the T1D research subject. Certification of their skill level is supervised by the study Nurse Manager. Other medical personnel may be licensed Emergency Medical Technicians. All medical personnel who will have direct contact with the study subject have current certification in Basic Life Support including CPR and AED. Study physicians will be available during the trial.

I. STOPPING RULES

Entire study

The study will be stopped if three similar AE's occur that are deemed moderate or severe or if there is system communication failures, which may trigger revision of the system software. Additionally, the Principal Investigator, IRB-HSR, Safety Officer, or sponsor may decide to stop the trial or part of the trial at any time. In this case, the Principal Investigator will promptly inform the subjects and assure appropriate therapy and follow-up. Additionally the Principal Investigator will notify the IRB if the study is temporarily stopped. The pertinent regulatory authorities will be informed according to national regulations.

Early study stop will be documented and following information will be collected:

- Date and cause of the ending

- Description of any serious adverse event leading to the study ending

A subject who does not complete the protocol may be replaced or rescheduled. Available data will be exploited.

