- SMBG >300 mg/dL for more than 2 hours during the experimental session
- SMBG \geq 400 mg/dL at any time during the experimental session
- The subject develops emesis, nausea and abdominal pain during the experimental session.
- Confirmed β -ketone level \geq 0.6 mmol/L for more than 2 hours during the experimental session
- Confirmed β -ketone level >1.5 mmol/L at any time

- System is in 'Stopped Mode' for more than 2 consecutive hours during the experimental sessions
- The subject has a positive pregnancy test.

Subjects who were not able to complete the study for reasons other than a serious adverse event (i.e. hypoglycemic seizure, etc.) will be permitted to repeat the session.

Reason Study Stopped	Repeat Session?
Equipment Failure or similarly related issues that invalidate study data	Can repeat session
Hyperglycemic Events that did not result in Serious Adverse Event	Can repeat session
Hypoglycemic Events that did not result in Serious Adverse Event	Can repeat session
PI initiated discontinuation of study due to patient or equipment concerns	Can repeat session
Serious or unanticipated adverse event deemed related to the study	Unable to repeat session

Table 1: Repeat Session Table

CATASTROPHIC EVENT PLAN

The Outpatient Emergency Plan will go into effect should a catastrophic event occur during the experimental session. A catastrophic event is defined as any event that requires emergency treatment by medical professionals that exceed the expected parameters of the protocol. A copy of this plan will be located at the monitoring desk. Staff will be aware of its location at all times.

Event	RN Response	Tech Response
Respiratory Arrest	1) Tell Tech to call 911 2) Begin Basic Life Support	Refer to Study Physician on-site
Cardiac Arrest	1) Tell Tech to call 911 2) Begin Basic Life Support	Refer to Study Physician on-site
Severe Hypoglycemic Event as defined by hypoglycemia accompanied by unconsciousness or seizure	1) Tell Tech to call 911 2) Administer glucagon IM (described in Hypoglycemia Safety	Refer to Study Physician on-site
Severe Hyperglycemic Event as defined by β -ketone level ≥ 0.6 mmol/L for >2 hours or >1.5 mmol/L, or symptoms of vomiting or abdominal pain are present	1) Discuss correction dose of insulin to administer s.c. via syringe with study M.D. 2) Encourage p.o. water intake	Refer to Study Physician on-site

Table 2: Outpatient Emergency Plan

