All adverse events	FDA	Annually	IDE annual report

Table 3: Reporting Table

E. Definition of a Protocol Enrollment Exception

An enrollment exception is the sponsor's prospective approval for the enrollment of a research subject that fails to meet current IRB-HSR approved protocol inclusion criteria, or falls under protocol exclusion criteria. Enrollment exceptions only apply to a single individual. Such a request should be rare and justified

in terms of serving the best interests of the potential study participant. Enrollment exceptions will be evaluated by the study medical monitor prior to enrollment.

F. Definition of a Data Breach

A data breach is defined in the HITECH Act (43 USC 17932) as an unauthorized acquisition, access, or use of protected health information (PHI) that compromises the security or privacy of such information.

G. Data Collection

Identifiable endpoint data be collected/recorded in the form of source documents and will be stored on a database on a Health Systems Computing Services (HS/CS) secure managed server that is configured to store PHI. De-identified data will be stored on password-protected network.

Safety Data Oversight will be completed by the Study Medical Monitor or designee. The medical monitor's designee will be a staff member from the institutional Clinical Trials Office. Monitoring Form example presented in Appendix A-11.

The PI will conduct an aggregate review of the following data:

- All adverse events
- Unanticipated Problems
- Protocol violations
- Audit results
- Early withdrawals
- Endpoint data

Other: In addition to the above, the reports will include subject enrollment. The principal investigator will also include the results of the safety reviews in the annual progress reports submitted to the IRB.

The annual report will address:

- Whether adverse event rates are consistent with pre-study assumptions
- Reason for dropouts from the study
- Whether all subjects met entry criteria
- Whether continuation of the study is justified
- Conditions whereby the study might be terminated prematurely

The relevant device regulation for reporting adverse events to the FDA will also be followed.

Data from each subject will be reviewed by the PI after completion of participation to determine whether the DiAs system was working properly and whether there were safety concerns.

IRB-HSR will be updated annually on the IRB-HSR continuation status form.

H. Adverse Events / Unanticipated Problems

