Recording, Reporting, and Grading

Only adverse events that are deemed related AND serious will be recorded, reported, and graded. The principal investigator will be responsible for the overall safety monitoring of the study. He, along with the sub-investigators, will review the individual adverse events as they occur. Any event that merits adverse event report will be collected and recorded in the IRB database by completing the IRB Adverse Event Reporting form online. The principal investigator can then use this database to produce a report of all adverse events reported on the study to do an aggregate review. If the AE is unexpected and serious, a signed hard copy of the IRB Adverse Event Reporting form will be submitted to the IRB within 7 calendar days.

I. Grading of Adverse Events

- Mild/Moderate/Severe
- Serious/Not serious
- The PI will determine the relationship of adverse events to the study using the following scale:
 - Related: AE is clearly related to the intervention
 - Possibly related: AE may be related to the intervention
 - Unrelated: AE is clearly not related to intervention

Reporting/recording of adverse events/unanticipated problems will begin after the subject begins study drug/device placement/intervention/study-related procedure/specimen collection.

Reporting/recording of adverse events/unanticipated problems will end at the end of study drug/device/intervention/participation.

VI. INSTITUTIONAL REVIEW BOARD DESCRIPTION

Institutional Review Board description is presented in Appendix A-12.

VII. LABELING

"CAUTION-Investigational Device. Limited by Federal (or United States) law to investigational use."

The investigational device is a system comprised of FDA-Approved and investigational component devices. The intended use of the system is the regulation of blood glucose levels in Type 1 diabetes via subcutaneous continuous glucose monitoring (CGM) and subcutaneous delivery of insulin. The use of the system is strictly limited to the clinical testing of a closed-loop control algorithm in controlled outpatient conditions.

- The FDA-Approved component devices that are used without modification are:
- Dexcom Gen4® Plus, Dexcom Inc. (PMA Number P050012)
- Roche Accu-Chek Spirit Combo insulin pump (PMA Number K111353).

We certify that we have copies of all product labeling for each approved/cleared device, which are available to any end-user/healthcare provider upon request.

The investigational component devices are:

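### The study-wide stopping rule counts moderate or severe adverse events whether or not they are serious, but the recording rule grades only events that are both related and serious

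*Combined protocol and SAP*

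**What the plan says.** - **Trigger.** Section I.I, Entire study: "The study will be stopped if three similar AE's occur that are deemed moderate or severe". Neither seriousness nor relatedness is a condition.
- **Recording.** Section V.H, Recording, Reporting, and Grading: "Only adverse events that are deemed related AND serious will be recorded, reported, and graded". The same paragraph says that the principal investigator and sub-investigators "will review the individual adverse events as they occur". It takes the aggregate review from the IRB database of reported events.
- **Scales.** Section V.I lists mild/moderate/severe and serious/not serious as two separate gradings. It has three relatedness levels: related (the link is clear), unrelated, and "Possibly related: AE may be related to the intervention".
- **What is to be reviewed and reported.** Section V.G puts "All adverse events" first among the items for the principal investigator's aggregate review. The last row of Table 3 sends the same category to the FDA yearly, in the "IDE annual report".
- **Events foreseen.** Table 1 (Repeat Session Table) allows a repeat session after "Hypoglycemic Events that did not result in Serious Adverse Event" and "Hyperglycemic Events that did not result in Serious Adverse Event".

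**The concern.** The trigger and the recording rule cover different sets of events. A rule that counts moderate and severe events needs a severity grade on every event that could count. The recording sentence withholds that grade from any event that is not serious. It may also withhold it from an event judged only possibly related, because V.I reserves the word related for a clear link.

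This is the study-wide adverse-event trigger for an investigational insulin-delivery system. The repeated, similar, non-serious events it should pick up include the glucose-related session stops that Table 1 foresees. If staff apply V.H as written, the plan provides no graded tally to show whether the third similar event has occurred. The aggregate review and the FDA annual report would also fall short of the full set of events they are meant to cover.

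**Working it through.** The plan states no rate, power or error figure for this rule, so there is nothing to reproduce. The check is a comparison of texts, followed by an illustration on assumed rates.

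**Step 1: one event traced through the text.** Take a session stopped for an SMBG below 45 mg/dL (Subject Withdrawal Criteria) that does not become a serious adverse event. Suppose the investigator considers it moderate.

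| Provision | Does it cover this event? |
|---|---|
| V.A, definition of an adverse event (any adverse finding) | Yes |
| I.I, stopping count | Yes, if similar to two others |
| V.H, recorded and graded | No, because it is not serious |
| V.H, aggregate report from the IRB database | No, because it draws on reported events |
| V.G, list for aggregate review | Yes |
| Table 3, annual FDA report | Yes |

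The V.H recording sentence, and the report built on it, are out of line with the other four provisions. V.I is also at odds with that sentence: if only related and serious events were graded, its not-serious and unrelated categories would never be used.

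**Step 2: how easily three events could arise.** Inputs: 36 completers (I.C) and the threshold of three (I.I). The per-session rate p of one event type is an assumption. Three events in three different subjects is 3/36 = 8.3% of subjects. With independent sessions, X ~ Binomial(n, p) and

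P(X ≥ 3) = 1 − P(0) − P(1) − P(2).

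For n = 36 and p = 0.05: 1 − 0.158 − 0.299 − 0.275 = 0.268.

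| Assumed p | Expected events, 36p | P(X ≥ 3), 36 experimental sessions | P(X ≥ 3), 72 sessions |
|---|---|---|---|
| 2% | 0.72 | 3.5% | about 17.5% |
| 5% | 1.8 | 26.8% | about 70.5% |
| 10% | 3.6 | 71.2% | about 97.9% |

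The last column adds the 36 control sessions at the same rate. The stopping rule does not confine the count to the experimental arm.

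**Step 3: what the recorded count would show.** Suppose a fraction f of these events is related and serious. The recorded count is then Binomial(36, pf). At p = 10%, where full capture gives 0.71, the chance that the recorded count reaches three is 0.27 for f = 0.5, 0.06 for f = 0.25 and 0.006 for f = 0.1. If none is serious, it is zero by construction. Both p and f are assumed, and the finding does not depend on them.

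**The case against.** The best defence is that the rule can still operate. It speaks of events deemed moderate or severe, which asks for a judgement and does not say that a recorded grade is needed. Investigators review events as they happen. Section V.G has the principal investigator review each subject's data for safety concerns after participation, and gives safety oversight to the medical monitor or a designee. Medically qualified staff attend the whole experimental session, and the system stores session data. Related severe hypoglycemia with seizure would largely be recorded already, since the Subject Withdrawal Criteria treat a hypoglycemic seizure as a serious adverse event. Subject-level and discretionary stops also exist. Finally, the V.H sentence is followed by text about the IRB database and may be a loosely worded filter on IRB reporting.

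Much of this stands. A reader might infer that repeated non-serious events would go unnoticed, or that the trigger would rest on memory alone. The documents do not support that: glucose-related stops leave traces that are reviewed subject by subject. What may be missing is the severity grade and the tally, not the event. The case report forms and monitoring form (Appendices A-9 and A-11) are not in the supplied text and may capture more.

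The defence does not remove the contradiction. None of these safeguards specifies a severity-graded count of similar events. If V.H was meant only as a filter on IRB reporting, it should say so, because as worded it governs recording and grading too.

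**Conclusion.** The concern holds as an inconsistency in the current text that affects the working of a safety rule. The wording conflict is certain. Its practical effect is not, because other reviews may bring the events to light and the unseen forms may record them.

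The supported conclusion is that, under a literal reading of V.H, non-serious moderate or severe events have no recorded grade, and the plan specifies no graded count from which to apply the study-wide trigger. The size can only be illustrated: the 3.5% to 71.2% range assumes independent sessions, one event type and per-session rates of 2% to 10%, none of which the documents give. The point should be corrected, but the documents do not show that the study lacks safety oversight.

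**What to change.** 1. In V.H, replace the restricting sentence with: *All adverse events, serious or not, will be recorded and graded for severity, seriousness and relatedness; expedited reporting follows Table 3.*
2. In I.I, Entire study, add: *The count of three includes non-serious events.*

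Leave the threshold of three as it is. Whether the count should be limited to related events is for the sponsor to decide. If the sponsor meant only related serious events to count, I.I should say that instead.

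**Cost.** One sentence replaced, one added, and an amendment; no new visits or measurements. There would be somewhat more recording and grading, and the stop might be triggered more often. The table under working shows how often for one event type, and the 72-session column applies if control sessions count. Pilot and substudy events would add to this. A stop is not easily undone: under I.I, resuming requires a problem that a change to the protocol or system can correct, plus FDA and IRB permission. Three similar but unrelated illnesses might leave nothing to correct, so the sponsor should settle the relatedness question in the same amendment.

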The studies will be conducted at UVA and will require IRB approval prior to the initiation of the trial. Thirty-six subjects with Type 1 Diabetes Mellitus will be needed to complete the protocol.

Based on our experience with similar studies, we estimate an expected 20-30% screen failures, dropouts, or withdrawals (7 to 10 subjects at UVA); thus we intend to set a recruiting target of 45 subjects. One pilot subject will be enrolled to test system performance. More than one subject may be admitted at one time.

Specific Aim 1 (SA1): Hypoglycemic risk, Open vs. Closed Loop (exercise)

Specific Aim 2 (SA2): Time within target range, Open vs. Closed Loop control during the day

Specific Aim 3 (SA3): Time within target range at night

Specific Aim 4 (Substudy/exploratory): Assess the effect size of Control Modules 1+3 (SSM+BRM) preventing nocturnal hypoglycemia and increasing time within target (80-140mg/dl) overnight as compared to CGM-augmented pump alone.

The testing of the three specific aims of the main study (SA1, SA2, SA3) involves different periods of time as presented in Figure 3. Thus, in addition to complete data, availability of partial data would allow testing some of the study hypotheses. As a general rule, a session will be considered useful for data analysis if the subject completes more than 80% of the active study protocol (29 out of 36 hours for the experimental session). Sessions completing less than 80% of the protocol will be rescheduled. Specifically, comparing risk and occurrence of hypoglycemia during the 5-hour periods encompassing exercise (14:00-19:00) on open- vs. closed-loop control will address SA1. Comparing the time within target range (70-180mg/dl) during the day (7:00-23:00) on open- vs. advisory control will address SA2, and comparing the time within target range (80-140mg/dl) and the risk for hypoglycemia overnight will address SA3 (Figure 2).

To determine sample size we used power analysis based on data from our previous closed-loop control studies, which showed significant reduction in hypoglycemia (due to Module 1) and increase in time within target during the day and overnight [15]. With N=36 subjects, the power for proving SA1 is 97% and the power for SA3 is similar, while the power for SA2 is lower, but sufficient - 85%. The significance level was reduced to $p=0.01$ to account for multiple comparisons.

[figure not shown]

Figure 2: Experimental vs. Control sessions

D. Study Duration

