11. The study subject will be instructed to follow a similar hypoglycemia and hyperglycemia safety protocol as the experimental session (the Home Glycemic Safety Protocol, Appendix A-6).
12. In addition to device-required calibrations, an additional calibration will be performed prior to the evening meal +/- 30 minutes to minimize the likelihood that a calibration is requested close to the time of the study meal. The CGM will be calibrated per manufacturer's guidelines with the study glucometer.
13. The subject will have access to ad lib glucose-free beverages.
14. The study subject will continue with the data collection process as described during Days 1-5.
15. Study personnel will be in frequent contact with the study subject during this phase of the study.
16. The study subject will be asked to confirm the time and content of meals and snacks when they occur. They will also notify study personnel of SMBG values.
17. Study subject will be asked to be at home with comparable physical activity level as the experimental session.
18. The study subject will return to the office on approximately Day 7. Data will be downloaded from all devices.

Pilot Session:

Up to two subjects will participate in a pilot experimental session. These subjects will follow the same procedures as Outpatient Study Visit for Continuous Glucose Monitor (CGM) Training. Data Collection Period (Days 1-5) does not need to be collected. Procedures for Pilot Session will be the same as and are described in "Procedures for the Experimental Session" *except for the procedures detailed below*. A pilot subject may also participate in 40-hour trial.

- Closed loop (AAA) will be initiated at 19:00 and proceed through Day 2 at 17:00 (22 hours). Components of the AAA system will be active at the same corresponding times within that timeframe:
 - SSM and BRM will be active throughout the study period (19:00 Day 1 through 17:00 Day 2).
 - AM will be active 19:00 Day 1 through 23:00 Day 1 and 7:00 Day 2 through 17:00 Day 2.
 - The same procedures will be followed as described in "Procedures for the Experimental Session".
- Discharge will begin at 17:00. The DiAs will stop AAA control. The system components (CGM sensors, study pump) will be removed.
 - The subject will resume his/her normal home pump therapy.
 - A fingerstick value will be obtained.
 - The subject will be discharged by approximately 18:00 if the following 3 conditions below are met:
 - the fingerstick value is 80-249 mg/dL

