6. Dinner will occur between approximately 18:00-19:00.
7. Hypoglycemic treatments can occur at any time per the subject's request. In addition, the Home Glycemic Safety Protocol will be followed by the study subject.
8. The subject will be started on DiAs in open loop mode between 20:00 – 22:00. When DiAs is operating, the Accu-Chek Aviva Combo Device is not paired to the pump and is unable to communicate with the pump. The subject will use the One Touch Ultra 2 or Aviva Combo glucometer for fingersticks while the DiAs is operating.
9. Subject may administer correction boluses per their usual regimen at any time prior to closed loop control initiation which is approximately 23:00.
10. The system will turn on SSM+BRM at 23:00 to 07:00.
11. At approximately 23:00, lights will be turned out, and the subject will be encouraged to sleep.

12. The staff will be checking the readings of the secondary CGM receiver at 03:00 AM and 05:00 AM during the night and will monitor remotely the subject.
13. CGM will be calibrated in the same manner as described in Procedures Related to the Experimental Session.
14. The subject will be awakened shortly before 7:00 AM and allowed time for routine hygiene.
15. A fingerstick value will be obtained upon waking while the subject is still fasting.
16. At 7:00 AM, DiAs will be stopped and the subject will resume CGM-augmented insulin pump therapy. These same procedures will be repeated for 5 consecutive nights. Subjects will be able to leave the CDT each morning if SMBG is 80-249 mg/dL, and glucose trend is stable. A meal will be offered.

Procedures Related to Discharge (Day 6 of substudy)

1. The subject will be awakened shortly before 7:00 AM and allowed time for routine hygiene.
2. A fingerstick value will be obtained upon waking while the subject is still fasting.
3. At 7:00 AM, DiAs will be stopped and the system components (CGM, pump) will be removed.
4. The subject will resume his/her normal home pump therapy.
5. A fingerstick value will be obtained.
6. The subject will be discharged by approximately 9:00 AM if the following 3 conditions below are met:
 - a. the fingerstick value is 80-249 mg/dL
 - b. the glucose trend is stable
 - c. Insulin on Board is appropriate as determined by the MD
7. If the subject's glucose is out of the specified parameters, the Hypoglycemia or Hyperglycemia Safety Protocol will be followed until the subject is in the specified range.
8. The subject will be offered a meal prior to discharge.

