The Accu-Chek Combo System is labeled for single-patient use. During the substudy when the Accu-Chek Spirit Insulin Pump is used in combination with the Aviva Combo Device, the system (the Aviva Combo device) will be single patient use. During the 2 day experimental session, the Accu-Chek Spirit Insulin Pump is not used with the Aviva Combo Device. In this configuration, the insulin pump is handheld. The subject interactions are primarily with the DiAs interface, not with the Accu-Chek Spirit Insulin Pump menu interface itself. Since there is no use of the Aviva Combo Device and minimal interaction with the handheld pump during the 2 day experimental session, the Accu-Chek Spirit Insulin Pump handheld device will be reused after cleaning adhering to hospital protocol as described below. All infusion set equipment will be single patient use only (infusion set insertion kits, tubing, cartridges etc.)

Cleaning Procedure: Equipment that touches intact skin will be cleaned with ethyl or isopropyl alcohol (70-90%), quaternary ammonium germicidal detergent (i.e. CaviCide) or household bleach. The contact time on the surface depends on the method used to clean the equipment. CaviCide requires three minutes on the surface. Clorox Germicidal Bleach Wipes require two minutes on the equipment. The surface should remain wet (i.e. slightly damp) with the disinfectant to be considered effective though not wet enough to leave drops of liquid. Equipment will be stored in a clean zipped bag.

The home glucose meters are single user devices.

Hb1Ac Risk: The University of Virginia central labs have College of American Pathologist (CAP) and the Clinical Laboratory Improvement Amendments (CLIA) certifications. While the central lab is not NGSP certified, the calibrators for the HbA1c assay are traceable to NGSP. The equipment (Tosoh G7) is NGSP

certified.

- Misuse Risk:

CGM training:

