In the case of an unanticipated adverse device effects (UADE), the overall study may be suspended while the problem is diagnosed and the PI investigates the UADE. If the PI determines that the UADE poses an unreasonable risk to subjects, the study should be suspended until this UADE can be resolved. If it cannot be resolved, the study should be terminated. Termination should occur no later than 5 working days after PI makes the decision. The result of the investigation and the PI's decision to terminate the study shall be reported the site IRB, and the FDA per 21CFR 812.46(b) (2). The medical monitor must determine if the UADE presents an unreasonable risk to subjects. If so, the medical monitor must ensure that all investigations, or parts of investigations presenting that risk, are terminated as soon as possible but no later than 5 working days after the medical monitor makes this determination and no later than 15 working days after first receipt notice of the UADE.

The study may resume if the underlying problem can be corrected by a protocol or system modification that will not invalidate the results obtained prior to suspension. The IRB will be notified if the study is stopped, and permission to resume will be obtained from the FDA and IRB prior to restarting.

SUBJECT WITHDRAWAL CRITERIA

An individual subject can be stopped from study participation at subject, PI, study MD, or sponsor's request.

The Principal Investigator, IRB-HSR, or Safety Officer may decide to stop the trial or part of the trial at any time. In this case, the Study MD will promptly inform the subject and assure appropriate therapy and follow-up. Additionally, the Principal Investigator will promptly inform the IRB and provide a detailed written explanation. The pertinent regulatory authorities will be informed according to national regulations.

The subject may request to be withdrawn from the study at any time for any/no reason. A subject will be withdrawn at the subject's request (withdrawal of informed consent) or at the request of the PI or sponsor.

Study procedures other than those required for subject safety would be stopped if:

- The subject had a serious adverse event deemed related to study.
- Glucagon is required to treat hypoglycemia.
- The subject experiences a hypoglycemic seizure.
- The subject becomes unconscious due to hypoglycemia.
- SMBG <45 mg/dL at any time during the experimental session

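### Six of the twelve subject-level stop criteria are worded for the experimental session only and do not expressly reach the substudy's closed-loop nights

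*Combined protocol and SAP*

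**What the plan says.** The Subject Withdrawal Criteria (Stopping Rules section) list twelve conditions under which study procedures not needed for safety are stopped. Six carry a session limit:

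- "SMBG <45 mg/dL at any time during the experimental session"
- "SMBG >300 mg/dL for more than 2 hours during the experimental session"
- SMBG of 400 mg/dL or more
- vomiting, nausea and abdominal pain
- ketone at or above 0.6 mmol/L for more than 2 hours
- Stopped Mode "for more than 2 consecutive hours during the experimental sessions"

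Six carry no such limit: related serious adverse event, glucagon use, hypoglycemic seizure, unconsciousness from hypoglycemia, ketone above 1.5 mmol/L, and a positive pregnancy test.

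The Catastrophic Event Plan uses the same limit: the Outpatient Emergency Plan "will go into effect should a catastrophic event occur during the experimental session".

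The substudy procedures (section G) allow five to eight subjects. Each spends five consecutive nights at the research house with SSM and BRM on from 23:00 to 07:00. DiAs is started in open loop between 20:00 and 22:00, and the study pump's own basal rate is programmed to 0 from that start until 07:00 (item 2).

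**The concern.** A limit to the experimental session makes sense for control days at home, when the subject is on their own pump. It does not fit the substudy nights, which put the subject on investigational overnight control with the same modules as an experimental night. Read literally, an SMBG below 45 mg/dL, an SMBG of 400 mg/dL or more, or more than two hours in Stopped Mode is a predefined stop on an experimental night. On a substudy night it is left to staff discretion or to appendices that are not part of the documents.

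The issue is subject safety and consistent conduct. Power and significance level are not affected.

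**Working it through.** The plan states no figure on this point. The check is a reading of the text plus a count of exposure.

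**1. Does the qualifier limit scope?** Yes. Within the same list, the ketone criterion at 0.6 mmol/L is tied to the session, while the one at 1.5 mmol/L applies at any time. Count: 12 criteria, 6 limited, 6 not.

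**2. Does the term include the substudy?** The usage points against it.

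- Section C (Sample Size) gives the session a fixed length: "29 out of 36 hours for the experimental session". That matches 19:00 on Day 5 to 07:00 on Day 7. Substudy nights are not part of those hours.
- Section H, under device reuse, contrasts the two settings. After describing pump use in the substudy it says: "During the 2 day experimental session, the Accu-Chek Spirit Insulin Pump is not used with the Aviva Combo Device".
- Where both settings are meant, both are named: section H does so for the overnight glycemic safety protocols and for DiAs training.
- The pilot takes over the experimental procedures in general terms: "Procedures for Pilot Session will be the same as and are described in" the experimental-session section. The substudy procedures take over one item only: "CGM will be calibrated in the same manner as described in Procedures Related to the Experimental Session".

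No sentence in the protocol or SAP extends the six criteria, or the Emergency Plan sentence, to the substudy.

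**3. Exposure.** Inputs: 5 to 8 subjects, 5 nights, 23:00 to 07:00 = 8 h (section G); 36 completers and 36 active hours each (section C); two experimental nights per subject; at most two pilot subjects, one night each (section G).

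- Substudy nights: 5 × 5 = 25 to 8 × 5 = 40.
- SSM+BRM hours: 25 × 8 = 200 to 40 × 8 = 320.
- Experimental active-control hours: 36 × 36 = 1,296.
- Share of active-control hours: 200/(200 + 1,296) = 13.4% to 320/(320 + 1,296) = 19.8%.
- Experimental nights: 36 × 2 = 72. Share of SSM+BRM nights: 25/(25 + 72 + 2) = 25.3% to 40/(40 + 72 + 0) = 35.7%.
- DiAs running time, relevant to Stopped Mode: 9 h per night if started at 22:00, 11 h if started at 20:00, so 25 × 9 = 225 h to 40 × 11 = 440 h.

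The hours share is the fairer overall measure, because the six criteria also protect the daytime part of the experimental session. The nights share compares like with like for overnight control. Repeated sessions would lower both. Neither says how often a criterion would be met.

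**4. What remains in force on substudy nights.** These safeguards apply:

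- the six unrestricted criteria;
- stops at the request of the subject, PI, study MD or sponsor;
- the study-wide rules on similar adverse events, communication failures and unanticipated device effects;
- the Hypoglycemia and Hyperglycemia Safety Protocols overnight;
- remote monitoring, the 03:00 and 05:00 checks, and the morning release check.

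The unrestricted clinical triggers are mostly later or more severe than the restricted ones. Seizure, unconsciousness, glucagon use and ketone above 1.5 mmol/L would generally follow, not precede, an SMBG below 45 mg/dL or a ketone of 0.6 mmol/L lasting two hours.

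**The case against.** The strongest reply is that care on these nights is already governed. Section H expressly extends the glycemic safety protocols to them. Their text (Appendix A-6) was not supplied and may itself direct a stop, and the DiAs manual (Appendix A-7) may cover Stopped Mode. This stands, and it confines the point to a scope gap in one list. It does not remove the gap, because the withdrawal criteria are the plan's own statement of when study procedures end.

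A second reply is that the term could be read broadly. Study Design speaks of experimental admissions in connection with closed-loop control, the 22-hour pilot is also called an experimental session, and the Stopped Mode criterion uses the plural. This is arguable, but the repeated separate naming of the substudy weighs more.

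A third is that the Emergency Plan wording changes little in practice. This is right. Staff with direct subject contact hold life-support certification, the safety protocols apply, and no scope phrase would keep them from calling 911. That part is editorial.

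Finally, the substudy is optional, small and exploratory, and no hazard specific to it has been shown. This is why the severity is low.

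**Conclusion.** The point holds as a minor gap in predefined stops. Six of twelve subject-level criteria do not, as worded, cover 25 to 40 substudy nights (200 to 320 hours) on the same overnight modules. That is about 13-20% of planned active-control hours, or 25-36% of SSM+BRM nights. The figures assume that the substudy enrolls its planned five to eight subjects, that 36 subjects complete the main study, and that no sessions are repeated.

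A reader might infer more in three ways, and the documents support none of them.

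- **Substudy subjects are unprotected at night.** The safeguards listed in the working contradict this.
- **A DiAs stop leaves the subject without basal insulin because the pump is programmed to 0.** The documents do not say how basal is delivered in Stopped Mode. The zero setting is a reason for a clear rule, not evidence of harm.
- **The exposure shares measure risk.** They measure time under control, not how often a criterion would trigger.

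**What to change.** In the six criteria, replace the session qualifier with the scope that section H already uses for the Hypoglycemia and Hyperglycemia Safety Protocols: the experimental session plus the substudy's overnight hours with SSM and BRM on. Let the Stopped Mode criterion run from DiAs start to 07:00, since the pump's own basal is 0 over that whole period.

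Keep all thresholds and the existing consequence: procedures not needed for safety stop, and repetition follows Table 1. Do not add a rule on basal insulin after a stop. A fixed instruction to resume usual basal would be unsafe after a low glucose, so insulin should follow the Hypoglycemia and Hyperglycemia Safety Protocols and the study MD. Do not limit a stop to a single night either, because that would soften the existing rule.

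As an editorial alignment, add the substudy overnight stay to the Emergency Plan's activation sentence.

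The cost is one amendment, with the IRB and regulatory approval that section VIII requires for safety-related changes, and possibly a few more stopped nights in exploratory aim SA4. If the sponsor already intends this coverage, the change only makes it explicit.
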